4.5.2. Pharmacokinetics Variables

Blood (plasma) samples will be collected for PK analysis and estimation of DHA exposure parameters. Approximately 10mLs (~2 mL/timepoint) of venous blood will be collected into fluoride-oxalate tubes from the arm opposite of that used for drug administration at pre- and 4 times after the first on-study dose in the hospital during different sampling windows. Sampling windows are defined as 0 (pre-dose), 0-1 hour, 1-2.5, 2.5-4, 4-6 and 6-24 hours post the first on-study dose of IV artesunate. Participants will be randomly assigned to either the 4-6 hour or the 6-24 hour collection timepoint via the Screening and Enrollment Log. All blood samples will be chilled immediately to prevent artesunate degradation by plasma esterases. Samples will be centrifuged within 30 minutes to minimize hemolysis, and aliquots of plasma will be stored at -80°C. Plasma aliquots will be shipped intermittently to the DMID-CMS (i.e., Fisher BioServices) for storage before quantification. Backup samples will be stored at the IDI Core Laboratory. Plasma samples will be analyzed by a validated liquid chromatographic-tandem mass spectrometry (LC-MS/MS) assay with measurement ranging from 1 to 3500 ng/mL (lower limit of quantification [LLOQ] to upper limit of quantification [ULOQ]).

Concentrations of DHA will be measured and used in estimating DHA exposure parameters, including maximum concentration (C_{max}), area under the curve over hours 0-12 (AUC_{0-12}), half-life ($t_{1/2}$) and time to C_{max} (T_{max}).

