8.2. Secondary Pharmacodynamics Analyses

8.2.1. Time to Hospital Discharge

We will perform secondary PD analyses to assess the relationship between measures of DHA exposure, including AUC_{0-12} , C_{max} , $t_{1/2}$ and T_{max} , and time to first hospital discharge. We will utilize Cox proportional hazards regression models for time to first hospital discharge and each DHA exposure parameter. Covariate selection (see Section 6.4 for a list of covariates that will be considered) for these models will be aided by exploratory boxplots of time to first hospital discharge by covariate, presented in [Figure 211](#) for participants in the PD Analysis Population.

The Cox proportional hazards regression model for time to hospital discharge and AUC_{0-12} , for example, would have cumulative hazard function

$$\Lambda(T_{HD} | AUC_{0-12,i}, X_i) = \lambda(T_{HD}) \times \exp\{\beta AUC_{0-12,i} + \eta^T X_i\},$$

where T_{HD} represents time to hospital discharge, $\lambda(T_{HD})$ is the baseline hazard function, X_i are the additional covariates included in the model, β is the expected change in the log hazard ratio relative to a one unit change in AUC_{0-12} holding the other covariates constant, and η is the vector of expected changes in the log hazard ratio comparing levels of the included covariates holding AUC_{0-12} and other covariates constant. The Cox

proportional cumulative hazard function for time to first hospital discharge and C_{\max} , $t_{1/2}$, or T_{\max} would be of the same form.

Models fit for the sensitivity analysis of the secondary analysis for time to hospital discharge using the subset of the PD Analysis Population who did not receive IV artesunate or other artemisinin-based therapy before enrollment will be of the same form as those fit in the secondary analysis for time to hospital discharge and the respective exposure parameter. Covariates included in each model fit for this sensitivity analysis will be those included in the respective secondary analysis model with effects that remain estimable in the sensitivity analysis subset. The type of model and covariates included for each analysis model will be presented in [Table 22](#) by PK exposure parameter for the PD Analysis Population and the subset of the PD Analysis Population that did not receive IV artesunate or other artemisinin-based therapy before enrollment.

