Summary statistics, including mean, SD, median, minimum, and maximum, for time to hospital discharge will be presented in [Table 20](#). Hazard ratios for time to hospital discharge corresponding to a one-unit change in exposure parameters adjusted for other covariates included in the models will be presented with corresponding 95% confidence intervals in [Table 21](#). Forest plots of hazard ratios and 95% CIs by exposure parameter will be presented for time to hospital discharge in [Figure 215](#).

The following pseudocode will be used to fit a Cox proportional hazard model for time to hospital discharge and estimate the hazard ratio for a one-unit increase in exposure along with its Wald confidence interval after adjusting for other covariates.

```
/* Fit Cox PH Model and Estimate Hazard Ratio for Exposure Parameter */
proc phreg data=dataset(where=(population=p));
*catvars = any categorical covariates included in the model;
*refvalues = the value(s) to be used as the reference level for categorical
covariate(s);
class catvars(ref=refvalues);
*othercovars = any other covariates (including those specified in the class statement)
included in the model;
model dischtime * censoringvar(1) = exposure othercovars / ties=breslow;
by timepoint;
hazardratio exposure / cl=wald;
ods output hazardratios = hrest;
run;
```

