Covariate selection for these models will be aided by exploratory boxplots of PCT_{50} and PCT_{90} by covariate in Figure 212 and Figure 213, respectively.

Models fit for the sensitivity analysis of the secondary analysis for PCT_{50} and PCT_{90} using the subset of the PD Analysis Population who did not receive IV artesunate or other artemisinin-based therapy before enrollment will be of the same form as those fit in the secondary analysis for the respective time to percent reduction parameter and exposure parameter. Covariates included in each model fit for this sensitivity analysis will be those included in the respective secondary analysis model with effects that remain estimable in the sensitivity analysis subset. The type of model and covariates included for each analysis model will be presented in Table 26 by parameter (PCT_{50} or PCT_{90}) and PK exposure parameter for the PD Analysis Population and the subset of the PD Analysis Population that did not receive IV artesunate or other artemisinin-based therapy before enrollment.

The Cox proportional hazards regression cumulative hazard function for PCT_{50} and PCT_{90} given AUC_{0-12} , C_{max} , $t_{1/2}$, or T_{max} will have the same form as that given in Section 8.2.1.

Hazard ratios for PCT_{50} and PCT_{90} corresponding to a one-unit change in exposure parameters adjusted for other covariates included in the models will be presented with corresponding 95% confidence intervals in

Table 25. Forest plots of hazard ratios and 95% CIs by exposure parameter will be presented for PCT₅₀ and PCT₉₀ in [Figure 216](#) and [Figure 217](#), respectively.

The relationship between exposure parameters (AUC₀₋₁₂, C_{max}, t_{1/2}, and T_{max}) and the binary variable of total parasite clearance by Day 2 will each be analyzed using logistic regression models. Covariate selection (see Section [6.4](#) for a list of covariates that will be considered) for these models will be aided by exploratory stacked bar charts of total parasite clearance by Day 2 by covariate, presented in [Figure 214](#) for participants in the PD Analysis Population.

The logistic regression model for total parasite clearance by Day 2 (Y) and AUC₀₋₁₂, for example, would be

$$\text{logit}(\pi) = \alpha + \beta \text{AUC}_{0-12,i} + \eta^T X_i,$$

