where $\pi = \text{Pr}(Y = 1 | \text{AUC}_{0-12,i}, X_i)$ is the probability of total parasite clearance by Day 2 adjusted for covariates X_i and $\text{AUC}_{0-12,i}$, α is the model intercept, β corresponds to the log odds ratio for a one unit increase in AUC₀₋₁₂ adjusted for other covariates, and η is a vector with components corresponding to the log odds ratio comparing levels of each additional included covariate holding AUC₀₋₁₂ and any other covariates constant. The logistic regression function for total parasite clearance by Day 2 and C_{max}, t_{1/2}, or T_{max} would be of the same form.

Models fit for the sensitivity analysis of the secondary analysis for total parasite clearance by Day 2 using the subset of the PD Analysis Population who did not receive IV artesunate or other artemisinin-based therapy before enrollment will be of the same form as those fit in the secondary analysis for total parasite clearance by Day 2 and the respective PK exposure parameter. Covariates included in each model fit for this sensitivity analysis will be those included in the respective secondary analysis model with effects that remain estimable in the sensitivity analysis subset. The type of model and covariates included for each analysis model will be presented in [Table 28](#) by PK exposure parameter for the PD Analysis Population and the subset of the PD Analysis Population that did not receive IV artesunate or other artemisinin-based therapy before enrollment.

Parasite density will be summarized by timepoint in [Table 23](#). The proportion of participants with total parasite clearance will be presented by timepoint in [Table 24](#). Individual parasite densities and parasite species identified from thick and thin blood smears, respectively, will be listed in [Listing 14](#).

Odds ratios for total parasite clearance by Day 2 corresponding to a one-unit change in exposure parameters adjusted for the confounding variable will be presented with corresponding 95% confidence intervals in [Table 27](#). Forest plots of odds ratios and 95% CIs for total parasite clearance by Day 2 by exposure parameter will be presented in [Figure 218](#).

The following pseudocode will be used to fit a logistic regression model for total parasite clearance by Day 2 and estimate the odds ratio for a one-unit increase in exposure along with its Wald confidence interval after adjusting for other covariates.

```

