13. REPORTING CONVENTIONS

P-values ≥ 0.001 and ≤ 0.999 will be reported to 3 decimal places, p-values less than 0.001 will be reported as “ <0.001 ”, and p-values greater than 0.999 will be reported as “ >0.999 ”. The mean, median, standard deviation, and other statistics will be reported to 1 decimal place greater than the original data. The minimum and maximum will use the same number of decimal places as the original data. Proportions will be presented as 2 decimal places; values greater than zero but <0.01 will be presented as “ <0.01 ”, and values less than one but >0.99 will be presented as “ >0.99 ”. Percentages will be reported to the nearest whole number; values greater than zero but $< 1\%$ will be presented as “ <1 ”; values greater than 99% but less than 100% will be reported as “ >99 ”. Estimated parameters, not on the same scale as raw observations (e.g. regression coefficients) will be reported to 3 significant figures.

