[figure not shown]
[Implementation Note: This is a sample figure. This figure will have panels for every exposure parameter (AUC₀₋₁₂, C_{max}, T_{max}, and t_{1/2}) and timepoint combination.]

Notes: Base = Baseline. 24 h and 48 h are measured from time of first dose of IV artesunate. EPD = End of Planned IV artesunate Dosing. THD = Time of first Hospital Discharge.
AUC₀₋₁₂ is measured in ng*h/mL, C_{max} is measured in ng/mL, T_{max} is measured in hours, and t_{1/2} is measured in hours.

Figure 13: Boxplots of Markers of Physiological Dysfunction by Covariate and Timepoint – PD Analysis Population, Temperature

[Implementation Note: This is a sample figure. This figure will have panels for every covariate (see Section 8) and timepoint combination. The y-axis label will be “Temperature (°C)”.]

Notes: Base = Baseline. 24 h and 48 h are measured from time of first dose of IV artesunate. EPD = End of Planned IV Artesunate Dosing. THD = Time of first Hospital Discharge. ConMeds = Receipt of Concomitant Medications. Prior Art. = Receipt of IV Artesunate or Other Artemisinin-based Therapy Before Enrollment.

Covariate Factor levels are as follows. Weight: {1 = <20 kg, 2 = \geq 20 kg}. Sex: {1 = Male, 2 = Female}. ConMeds: {1 = Did Not Receive Concomitant Medications, 2 = Received Concomitant Medications}. Prior Art.: {1 = No IV Artesunate or Other Artemisinin-Based Therapy Before Enrollment, 2 = Received IV Artesunate or Other Artemisinin-Based Therapy Before Enrollment}. Oral ACT: {1 = Did Not Receive Any Oral ACT, 2 = Received Oral ACT}.

Figures with similar format:

Figure 14: **Boxplots of Markers of Physiological Dysfunction by Covariate and Timepoint – PD Analysis Population, Systolic Blood Pressure**

Figure 15: **Boxplots of Markers of Physiological Dysfunction by Covariate and Timepoint – PD Analysis Population, Diastolic Blood Pressure**

Figure 16: **Boxplots of Markers of Physiological Dysfunction by Covariate and Timepoint – PD Analysis Population, Serum Lactate**

Figure 17: **Boxplots of Markers of Physiological Dysfunction by Covariate and Timepoint – PD Analysis Population, Serum Bicarbonate**

Figure 18: **Boxplots of Markers of Physiological Dysfunction by Covariate and Timepoint – PD Analysis Population, Serum Glucose**

Figure 19: **Boxplots of Markers of Physiological Dysfunction by Covariate and Timepoint – PD Analysis Population, Total Bilirubin**

[figure not shown]

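### Secondary hazard and odds ratios per one raw unit of AUC0-12 or Cmax can round to 1.0 or 1.00, and ratios above 1 lose more than ratios below 1

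*SAP*

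**What the plan says.** The scale is set explicitly for every secondary outcome.

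- **Discharge (SAP Section 8.2.1).** The plan is to present "Hazard ratios for time to hospital discharge corresponding to a one-unit change in exposure parameters". The Cox coefficient for AUC0-12 "is the expected change in the log hazard ratio relative to a one unit change in" AUC0-12, with exposure entered untransformed. The models for Cmax, half-life and Tmax have the same form. The code requests "hazardratio exposure / cl=wald", with no other increment.
- **PCT50 and PCT90 (Section 8.2.2).** Hazard ratios are "corresponding to a one-unit change in exposure parameters adjusted for other covariates included in the models".
- **Clearance by Day 2 (Section 8.2.2).** The plan is "Odds ratios for total parasite clearance by Day 2 corresponding to a one-unit change in exposure parameters". The logistic code also sets no increment.

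The figure notes in Appendix 2 say that AUC0-12 "is measured in ng*h/mL". Cmax is in ng/mL, and Tmax and half-life are in hours. The only indication of concentration scale is the DHA assay in Section 4.5.2, with "measurement ranging from 1 to 3500 ng/mL".

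On precision, the shells of Tables 21, 25 and 27 show ratios and limits as xx.x. Section 13 says that estimated parameters not on the scale of the raw observations "will be reported to 3 significant figures". Unlike primary Table 17, these three shells have no p-value column.

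**The concern.** If exposures differ between children by tens or hundreds of units, the ratio for one unit lies very close to 1 even when the effect across the observed range is large. Rounding can then remove the result. With no p-value alongside, a reader cannot recover the size of the effect or the strength of evidence from the table.

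The 3-figure rule adds an asymmetry. A ratio just below 1 keeps three decimals, while a ratio just above 1 keeps two. Slower and faster discharge or clearance with rising exposure would therefore not be shown equally well.

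Discharge and parasite clearance are the only two secondary objectives, and AUC0-12 and Cmax are the only two exposures that protocol Section 11.3.5 names for them.

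**Working it through.** **The plan's own figures.** No figure in either document concerns the scale of these ratios. The numerical design figures are the average powers in SAP Table 3. A simulation reproduces them (24 tests, 5% non-null, N=100, 80 and 70: 0.952, 0.876 and 0.796, against 0.95, 0.88 and 0.80), but they do not bear on this point.

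**Inputs.** The one-unit scale, the units and the two rounding formats come from the SAP. The exposure SD is assumed, because the documents do not give it. The hazard ratio (HR) per SD is set at 0.5, 1 or 2 for illustration. The standard error of the log HR per SD is taken as 1/√events. Enrolment is capped at 100, and 75 events are used below.

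**Formulas.** HR per unit = exp(ln(HR per SD)/SD). CI per unit = exp((ln(HR per SD) ± 1.96/√75)/SD), where 1.96/√75 = 0.226.

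| Assumed SD | HR per SD | HR per unit (95% CI) | One decimal | 3 significant figures |
|---|---|---|---|---|
| 25 | 2 | 1.02811 (1.01885, 1.03746) | 1.0 (1.0, 1.0) | 1.03 (1.02, 1.04) |
| 100 | 0.5 | 0.99309 (0.99085, 0.99534) | 1.0 (1.0, 1.0) | 0.993 (0.991, 0.995) |
| 100 | 2 | 1.00696 (1.00468, 1.00924) | 1.0 (1.0, 1.0) | 1.01 (1.00, 1.01) |
| 250 | 0.5 | 0.99723 (0.99633, 0.99813) | 1.0 (1.0, 1.0) | 0.997 (0.996, 0.998) |
| 250 | 2 | 1.00278 (1.00187, 1.00368) | 1.0 (1.0, 1.0) | 1.00 (1.00, 1.00) |
| 500 | 0.5 | 0.99861 (0.99816, 0.99907) | 1.0 (1.0, 1.0) | 0.999 (0.998, 0.999) |
| 500 | 1 | 1.00000 (0.99955, 1.00045) | 1.0 (1.0, 1.0) | 1.00 (1.00, 1.00) |
| 500 | 2 | 1.00139 (1.00093, 1.00184) | 1.0 (1.0, 1.0) | 1.00 (1.00, 1.00) |
| 1000 | 0.5 | 0.99931 (0.99908, 0.99953) | 1.0 (1.0, 1.0) | 0.999 (0.999, 1.00) |
| 1000 | 2 | 1.00069 (1.00047, 1.00092) | 1.0 (1.0, 1.0) | 1.00 (1.00, 1.00) |

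**One-decimal threshold.** A ratio prints as 1.0 when it lies between 0.95 and 1.05 per unit. At SD 25 that covers point estimates from 0.28 to 3.4 per SD, and at SD 100 from 0.006 to 132. At SD 10 it covers only 0.60 to 1.63, so an HR of 2 per SD would print as 1.1 (exp(0.693/10) = 1.07).

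**3-figure threshold.** A ratio prints as 1.00 when it lies between 0.9995 and 1.005 per unit.

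- HR 2 per SD prints a point estimate of 1.00 once SD > ln 2/ln 1.005 = 0.6931/0.0049875 = 139.
- HR 3 per SD does so once SD > 1.0986/0.0049875 = 220.
- HR 0.5 per SD does so only once SD > 0.6931/0.000500125 = 1386, about ten times the SD needed for HR 2.

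**Check on fitted models.** Cox fits (Breslow ties) to simulated raw exposures with N=100 agree. At SD 380, a fitted HR per SD of 1.95 (1.56, 2.44), p = 5.7e-09, printed as 1.0 (1.0, 1.0) and as 1.00 (1.00, 1.00). At SD 500, a null simulation with fitted HR per SD 1.13 (0.90, 1.41), p = 0.28, printed the same in both formats. Logistic odds ratios behave alike, with somewhat wider limits: near SD 20 a limit could still print as 0.9 or 1.1, but at SD 34 and above every fitted odds ratio printed 1.0 (1.0, 1.0) at one decimal.

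**The case against.** Four points can fairly be made on the other side.

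- **The shells may not be literal.** Table 17 uses the same xx.x for primary regression estimates, yet the sample equations under Figures 35 and 36 show coefficients such as -0.0061 and 0.0177, which one decimal would reduce to 0.0. Section 13 is the only written rounding rule. This stands as a reason not to rest the point on one decimal alone, but the shells and Section 13 still need to be aligned.
- **Strong and null effects need not look alike.** A reader might infer that AUC0-12 and Cmax results would print as 1 whatever the truth. Under the 3-figure rule that is not so. With a standard error of 0.25 and SD 300, HR 0.5 per SD prints as 0.998 (0.996, 0.999) and HR 0.33 as 0.996 (0.995, 0.998), both visibly excluding 1. Below an SD of about 139, HR 2 per SD also prints above 1.00. This stands.
- **The SD is unknown.** The 1 to 3500 ng/mL range belongs to the assay and does not show how much children differ. This stands, which is why thresholds are given here rather than a single figure.
- **The forest plots may help.** It is tempting to say that Figures 215 to 218 could not show an effect. Plots need not use rounded values, and the sample graphic is not visible in the text available. The notes establish only that all four exposures share a figure and that units will be labelled.

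The objection also notes that these are secondary analyses, without multiplicity adjustment, in a study that the SAP calls exploratory. That bears on priority, not on whether the tables can be read.

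**Conclusion.** The point holds as a reporting defect for two of the four exposures in all the secondary analyses. Following the plan as written can print a strong AUC0-12 or Cmax effect as 1.0 (1.0, 1.0), on a literal reading of the shells with an SD of about 25 or more. It can print one as 1.00 (1.00, 1.00) at 3 significant figures, for HR 2 per SD with an SD of about 250 or more. At 3 significant figures ratios below 1 remain visible over a much wider range of SDs, so direction is shown unequally and size is hard to read in either direction.

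These figures rest on an assumed exposure SD and on approximate standard errors. The documents do not support the stronger claims that every result would print as 1 or that the forest plots would be uninformative. No estimate, interval or test is biased, and Tmax and half-life, reported per hour, are not affected.

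**What to change.** Report all secondary hazard and odds ratios per IQR or per SD of each exposure in the PD Analysis Population, or per a prespecified fixed increment. Print the increment, use two decimals, and apply the same scale in Tables 21, 25 and 27 and Figures 215 to 218. In code, use the UNITS= option in the PHREG HAZARDRATIO statement and a UNITS statement in LOGISTIC. Align the shells with Section 13.

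With 75 events, HR 2 per SD would then read 2.00 (1.59, 2.51), from exp(0.693 ± 0.226), and HR 0.5 would read 0.50 (0.40, 0.63).

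The cost is SAP and shell wording. Models, tests and populations do not change. The drawback is that an IQR or SD depends on the sample, so its value must be printed for comparison with other studies; a fixed increment avoids this. Settling the scale before results are seen also avoids a SAP deviation that the interim CSR would have to justify.

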4.5. Pharmacodynamics, Pharmacokinetics, Immunogenicity, and Safety Variables

4.5.1. Pharmacodynamics Variables

The primary PD outcome response variables are temperature, blood pressure, serum lactate, serum bicarbonate, serum glucose, total and direct bilirubin, hemoglobin, creatinine, and BCS.

BCS is an ordinal scale designed to assess malarial coma in children. Eye movement, best motor response, and best verbal response are assessed and scored according to the evaluation criteria presented in the table below. The BCS is then calculated as the sum of the scores for these three assessments, with possible values of 0, 1, 2, 3, 4, or 5. Lower BCS values are indicative of impaired consciousness.

Assessment	Evaluation Criteria	Score
Eye Movement	Watches or follows – 1 Fails to watch or follow – 0	0 or 1
Best Motor Response	Localizes painful stimulus – 2 Withdraws limb from painful stimulus – 1 No response or inappropriate response – 0	0, 1, or 2
Best Verbal Response	Cries appropriately with pain, or, if verbal, speaks – 2 Moan or abnormal cry with pain – 1 No vocal response to pain – 0	0, 1, or 2
Total Score		0, 1, 2, 3, 4, or 5

Primary PD outcome response variables will be recorded at least daily for each patient while hospitalized and at scheduled follow-up visits according to the schedule in [Table 2](#).

Dates and times of hospital admittance and discharge for each participant will be collected on the appropriate eCRF for calculation of time to hospital discharge. Time to hospital discharge is defined as the time in days from initial participant admission to the time of first discharge. Time to hospital discharge will be calculated using the actual dates and times of initial participant admission and first discharge and will be rounded to the nearest tenths place.

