5. SAMPLE SIZE CONSIDERATIONS

A maximum of 100 participants will be enrolled in the study. This maximum of 100 participants would provide sufficient sample size to achieve precision on PK parameters following the FDA pediatric precision criteria for conducting PK studies (achieving a 95% confidence interval (CI) within 60% and 140% of the geometric mean).

Simulations in R version 3.4.2 were used to explore power to detect simple linear relationships between exposure and response in the analysis of the primary objective with the planned sample size. The primary objective of this study is to determine the relationship between DHA exposures after IV dosing and markers of physiologic dysfunction associated with severe malaria. This objective can be framed as a series of statistical hypothesis tests, each evaluating the effect of the DHA exposure parameter on the marker of physiologic dysfunction measured at a specific timepoint, adjusting for covariates. The null hypothesis is that there is no effect of exposure on response, and the alternative hypothesis is that there is an effect.

Because the primary objective of this study encompasses multiple exposure and response variables, and the response variables are measured at multiple timepoints, there are multiple exposure-response relationships that are of interest (one for each unique combination of exposure variable, response variable, and timepoint). Thus, there is a need to control type I error. As this study is exploratory (hypothesis-generating) rather than confirmatory, Benjamini-Hochberg procedure is used to control the false discovery rate at 0.05 [Table 5].

For a multiple hypothesis test, average power is defined as the proportion of false null hypotheses correctly rejected [6]. Table 3 provides the average power computed from 5000 simulations, varying the following quantities:

- Number of total statistical tests, representing the number of combinations of exposure variable, response variable, and timepoint to be tested in support of the primary objective
- Value of R^2 for the true, non-null exposure-response relationships
- Proportion of tests with true, non-null exposure-response relationships with the specified R^2
- Sample size

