Sample sizes considered in these simulations included 100 or 80 participants. These original simulation results indicate that the target sample size of 100 participants provides >90% power for detecting simple linear relationships for 24 or 48 tests with an underlying R^2 of at least 0.2, if the proportion of non-null relationships among those tested is at least 5%. If at least 80 participants complete follow-up for the primary outcome measure, power for the same scenario is approximately 88%.

However, at the end of the planned enrollment period of 6 months, only 46 participants had been enrolled in the study. Further simulations were performed under the same settings described above with smaller sample sizes considered. These results are also provided in Table 3. These simulation results indicate that if at least 70 participants complete follow-up for the primary outcome measure, power for detecting simple linear relationships for 24 or 48 tests with an underlying R^2 of at least 0.2, if the proportion of non-null relationships among those tested is at least 5%, is $\geq 80\%$.

Additionally, given that there are eleven markers of physiological dysfunction, four exposure parameters, and four timepoints (see Section 8.1) of interest, the total number of possible hypothesis tests for all of these relationships is 176. Further simulations were performed under the same settings described above with 176 tests and sample sizes of 75, 80, or 90 participants considered. These results are also provided in Table 3. These simulation results indicate that if at least 75 participants complete follow-up for the primary outcome

measure, power for detecting simple linear relationships for 176 tests with an underlying R^2 of at least 0.2, if the proportion of non-null relationships among those tested is at least 5%, is greater than 80%.

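### Time-to-discharge Cox model: Breslow ties on times rounded to 0.1 day shrink a real log hazard ratio by about 2-4%, and ties=efron removes this at no cost

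*SAP*

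**What the plan says.** SAP section 4.5.1 records clock times: "Dates and times of hospital admittance and discharge for each participant will be collected on the appropriate eCRF". The endpoint is a duration: "Time to hospital discharge is defined as the time in days from initial participant admission to the time of first discharge". It is computed from the actual dates and times "and will be rounded to the nearest tenths place". The rounding is part of the definition of the variable. Display precision is dealt with separately, in section 13.

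Section 8.2.1 gives the PROC PHREG code that is to be used, with the model line "model dischtime * censoringvar(1) = exposure othercovars / ties=breslow" and a Wald interval requested by "hazardratio exposure / cl=wald". Neither section gives a reason for the rounding or for Breslow, and no other tie method or sensitivity analysis on ties is planned. Section 8.2.2 gives the PCT50 and PCT90 Cox models the same form but shows no separate code for them.

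**The concern.** A tenth of a day is 0.1 × 24 = 2.4 hours. If most children go home within a few days, many will share a rounded discharge time although their recorded times differ. The plan thus creates ties that the collected data largely lack, then handles them with the approximation that ties bias most.

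Time to discharge is one of the two secondary objectives, and its hazard ratios and intervals are the reported result (Table 21, Figure 215). If exposure does affect discharge, those ratios would lie slightly too close to 1. The planned sensitivity analysis in children without prior artemisinin uses models of the same form, so it would not reveal this.

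**Working it through.** The documents state no hazard ratio, event count or power for this analysis, so there is no planned figure to reproduce. The power in SAP Table 3 concerns simple linear exposure-response relationships.

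**Inputs from the documents**
- Tie method Breslow (SAP 8.2.1); rounding to 0.1 day (SAP 4.5.1).
- Sample size: upper value 100 ("A maximum of 100 participants will be enrolled in the study"); lower value 46 ("only 46 participants had been enrolled in the study", at the end of planned enrollment); 75 as a middle value (all SAP section 5).
- At least 24 hours of IV treatment (Protocol Summary), used as a floor for the stay.

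**Assumptions, because the documents do not give these**
- Stay = 1 day + Weibull (shape 1.5), with median 2.5, 3 or 4 days; one variant with a 3-day median and discharge only between 09 and 13 h.
- True hazard ratio 1.30, 1.65 or 2.00 per SD of exposure.
- Every participant is discharged, so nobody is censored.

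**Formulas.** Take a time with d tied discharges, let S_R be the sum of exp(βx) over everyone still at risk, and S_D the same sum over the d tied participants.
- Breslow denominator: S_R raised to the power d.
- Efron denominator: product over l = 0, …, d−1 of (S_R − (l/d)·S_D).

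Breslow keeps all tied participants in the risk set for each of the d events, which pulls β toward 0. With d = 1 the two are identical.

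**Check.** In each scenario 1,000 data sets were fitted three ways: exact times, rounded times with Breslow, and the same rounded times with Efron. Shortfall = 1 − (mean log HR)/(mean log HR with exact times). Selected scenarios:

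| N | True HR | Median stay (days) | Tied | HR exact | HR Breslow | HR Efron | Shortfall Breslow | Shortfall Efron | Efron − Breslow, in SE |
|---|---|---|---|---|---|---|---|---|---|
| 46 | 1.30 | 2.5 | 66% | 1.312 | 1.299 | 1.311 | 3.6% | 0.4% | 0.05 |
| 46 | 2.00 | 4 | 42% | 2.044 | 2.017 | 2.042 | 1.9% | 0.1% | 0.07 |
| 75 | 1.65 | 3 | 71% | 1.659 | 1.637 | 1.658 | 2.6% | 0.1% | 0.09 |
| 75 | 2.00 | 3 | 69% | 2.008 | 1.971 | 2.006 | 2.7% | 0.1% | 0.12 |
| 100 | 1.30 | 4 | 69% | 1.306 | 1.300 | 1.306 | 1.7% | 0.0% | 0.04 |
| 100 | 2.00 | 2.5 | 83% | 2.022 | 1.970 | 2.019 | 3.7% | 0.2% | 0.20 |

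For the fourth row: 1 − ln(1.971)/ln(2.008) = 1 − 0.6785/0.6971 = 2.7%.

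**Across all 0.1-day scenarios**
- Participants tied: 42-66% at N = 46 and 66-86% at N = 100.
- Breslow shortfall 1.7-3.7%, toward HR = 1 every time; Efron shortfall 0.0-0.4%. A separate run at N = 46 and 100 gave 1.4-3.7% for Breslow and within about 0.5% for Efron.
- Gap between Efron and Breslow: 0.03-0.20 SE.
- Coverage of the 95% interval with Breslow: 94-97%.
- Loss of significant results: at most 3 points (38.1% to 35.1%; N = 46, HR 1.30, median 2.5 days).

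**Extreme bound.** With whole-day times the shortfall would be 23-24% for Breslow and about 4-6% for Efron. The SAP does not round that coarsely.

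**The case against.** The strongest objection is that this does not matter. The analysis is secondary, has no multiplicity adjustment and no decision rule, the Table 21 shell has no p-value column, and the SAP calls the study hypothesis-generating. A gap of at most 0.2 SE is small against the interval, and any bias is conservative. All of that stands.

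The reporting scale weakens the point further. Hazard ratios are given per one unit of exposure. The SD of exposure is not in the documents; suppose it is 100 to 1,000 units for AUC and Cmax (the assay range in SAP 4.5.2 is 1 to 3500 ng/mL). A ratio of 2.0 per SD is then exp(0.6931/100) = 1.0070 to exp(0.6931/1000) = 1.0007 per unit. With 3% taken off the log it is 1.0067 to 1.0007. These print alike at one decimal (the Table 21 shell) or three significant figures (SAP section 13). This also stands, but not for Tmax and t1/2, which are in hours. If their SD were 1 hour, the fourth row of the table would print as 2.01 against 1.97 at three significant figures.

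Two stronger readings are tempting, and the documents support neither. A reader might infer that every reported hazard ratio will be too close to 1. There is no bias when the true ratio is 1, and nothing in the documents establishes an effect of exposure on discharge. A reader might also infer that the rounding itself is the defect. Efron on the same rounded times is nearly unbiased, so the loss comes from Breslow acting on the ties.

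**Conclusion.** The point holds as a minor one. If an exposure effect on discharge exists, the planned code shrinks its log hazard ratio by about 2-4%, and inference is essentially unaffected. The direction follows from the method. The size rests on the assumed stays (medians of 2.5 to 4 days), 46 to 100 participants and hazard ratios of 1.3 to 2.0 per SD. Shorter or more clustered stays would give more ties and a larger shortfall.

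It also rests on taking section 4.5.1 at its word, so that the rounded value enters the model. If the programmer fits the unrounded time, almost all ties disappear and the choice hardly matters. The change is worth making because the bias, where it exists, goes one way and costs nothing to remove.

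**What to change.** In the time-to-discharge code of SAP section 8.2.1, replace ties=breslow with ties=efron. Do the same for the PCT50 and PCT90 Cox models of section 8.2.2 if they reuse that code; where no times are tied, the result is unchanged.

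The cost is one keyword. It needs no new data and leaves the sample size and the multiplicity plan as they are.

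Optionally, fit the unrounded duration that is already calculated and keep the 0.1-day rounding for tables. That is a separate edit to the definition in section 4.5.1, and it adds almost nothing once Efron is used.
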